### 6. GENERAL ANALYSIS DEFINITIONS

#### 6.1 **TREATMENTS**

For basic trial information on treatments to be administered, assignment of dose group, and selection of doses, see CTP Section 4.

Long Name	Short Name
Placebo	Placebo
BI 425809 2 mg QD	BI 2mg
BI 425809 5 mg QD	BI 5mg
BI 425809 10 mg QD	BI 10mg
BI 425809 25 mg QD	BI 25mg

Table 6.1: 1Treatment descriptions

 Table 6.1: 2
 Analysing treatment periods (same for all treatment groups)

Analysing Treatment Period	Start Date	Stop Date
Screening	Date of informed consent	Date of the first treatment administration
On-treatment	Date of the first treatment administration	Date of the last treatment administration + REP + 1 day
Follow-up	Date of the last treatment administration + REP + 1 day	Date of the last per protocol visit

REP is the residual effect period which is defined as 11 days after the last dose of trial treatment.

#### 6.2 IMPORTANT PROTOCOL DEVIATIONS

A protocol deviation (PD) is important if it affects the rights or safety of the study subjects, or if it can potentially influence the primary outcome measurement(s) in a non-negligible way.

A list of important PDs (IPDs) is given in Table 6.2: 1. Important PDs will be reviewed at Trial Oversight Meeting (TOM) conducted periodically during the trial. A list of protocol deviations (treatments are blinded) will be discussed at the Report Planning Meetings (RPMs) before data unblinding.

If the data show other important PDs, this table will be supplemented accordingly at TOMs or RPMs or through team review of the manual PD log. The decision whether a subject will be excluded from the analysis will be made at the final RPM prior to Database Lock (DBL).

## **Boehringer Ingelheim**

 TSAP for BI Trial No: 1346.9
 Page 15 of 34

 Proprietary confidential information © 2020 Boehringer Ingelheim International GmbH or one or more of its affiliated companies

Category/Code		Description	Example/Comment	Excluded from
Α		Entrance criteria not met	1	•
	A1	Inclusion criteria not met		
	A1.1	No diagnosis of Schizophrenia per DSM-5 or medically and psychiatrically not stable	IN3 in the CTP not met	PPS
	A1.2	Age <17 or >52	IN2 in the CTP not met. Check age in demographic page	None
	A1.3	Not exhibit reliability, physiologic capability or have insufficient educational level	IN6 in the CTP not met	None
	A1.4	No consistent informant identified	IN7 in the CTP not met	None
	A1.5	Violation of IN4	Either one of the first two bullet points in IN4 regarding typical and/or atypical antipsychotics use	None
	A2	Exclusion criteria met		
	A2.1	Any exclusion criteria met	EX1-EX29 in the CTP	None
	A2.2	Any of the exclusion criteria for the ophthalmologic sub-study met	See CTP Section 10.8.3.2	EYE
B		Informed consent		
	B1	Informed consent not available/not done		
	B1.1	Informed consent not available/not done	IN1. No patient signature on ICF. Not follow local law requirement for informed consent.	All
	B1.2	Ocular measurements taken without ICF for ophthalmologic sub-study	Signed ICF for main study available but not for ophthalmologic sub-study, but ocular measurements were taken; not an IPD if consent for the ophthalmologic sub- study was given late	EYE

#### Table 6.2: 1 Handling of IPDs

 TSAP for BI Trial No: 1346.9
 Page 16 of 34

 Proprietary confidential information © 2020 Boehringer Ingelheim International GmbH or one or more of its affiliated companies

#### Table 6.2: 1 Handling of IPDs (cont'd)

Category/Code		Description	Example/Comment	Excluded
				from
С		Trial medication and randomisation		
	C1	Incorrect trial medication taken		
	C1.1	Incorrect trial medication taken during study	Any deviation. Check whether the medication packages dispensed (med. numbers entered into RDC) has the correct content (to be seen from the med. number list that was the basis for packaging). If content was correct, the deviation will only be noted. Otherwise, the cases will be described individually and possibly excluded. In addition, check whether the dispensed packages match the randomised treatment of the patient (IVRS assignment). If not, and if treated consistently throughout the trial analyse as	None
			treated.	
	C2	Randomisation order not followed		
	C2.1	Error by the vendor who implemented the randomisation scheme	E.g., the same randomisation number was given to different patients or the assignment of duplicate medication numbers or incorrect medication numbers. Or wrong stratum. Verify by comparing the medication numbers and randomisation numbers from IVRS. If a patient actually receives the correct medication despite the wrong kit, such deviation will only be noted.	None
	C3	Non-compliance with trial medication		
	C3.1	<80% cumulative compliance rate with trial medication during the entire treatment period	<80% cumulative compliance rate with trial medication during the entire treatment period is considered as an IPD	None

 TSAP for BI Trial No: 1346.9
 Page 17 of 34

 Proprietary confidential information © 2020 Boehringer Ingelheim International GmbH or one or more of its affiliated companies

Category/Code		Description	Example/Comment	Excluded
	r			from
D		Concomitant medication		
	D1	Prohibited medication (including	All medications before first	None
		prohibited procedures) use before the	drug administration (those	
		first administration of trial medication	defined in CTP Section 4.2.2).	
			To be determined on a case by	
			case basis.	N T
	D2	Prohibited medication (including	As defined in CTP Section	None
		prohibited procedures) use during the	4.2.2. To be determined on a	
		period)	case by case basis.	
	D2.1	Used restricted medications within 8 hours	E.g., anticholinergic agents,	PPS
		before taking MCCB after Visit 1	antihistamine, benzodiazepine,	
		C C	benztropine,	
			diphenhydramine, sleep	
			medication	
	D3	Subjects who stopped taking all		None
		antipsychotics and refused to re-take		
		antipsychotics during the study		
F		Incorrect timing of endpoint measurement	ication	
	F1	Primary endpoint performed at		
		incorrect date/time		
	F1.1	MCCB measured outside the allowed time	MCCB should be performed at	None
		window	the same time of the day, i.e.	
			Within $\pm 120$ minutes at	
			visits 4 and / or EO1 as	
			administration time	
	F1 2	Baseline MCCB measured after first drug	Visit 2 MCCB should be	None
	1 1.2	administration	measured before the first drug	None
			administration	
	F1.3	EOT MCCB measured $>10$ days after last	E.g. EOT MCCB measured	None
		drug administration	>10 days after last drug	
			administration	
Ζ		Other		
	Z1	Serious issue of protocol deviation	Cases reported from site	None
			monitoring	
	Z2	Other protocol deviation affecting	E.g. substantial change in	None
		efficacy and possibly safety	nicotine consumption; positive	
			drug screening during study	
	Z3	Other protocol deviation affecting safety	E.g. abnormal hemoglobin	None
		only	measurement; not reported or	
			under-reported suicidal	
			ideation; DILI cases not	
			handled properly	

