7.3 PLANNED ANALYSES

The following patient analysis sets are defined for this trial:

- Treated Set (TS): includes all patients who signed informed consent and were treated with at least one dose of the trial medication. Patients in TS are analyzed under the actual trial medication received at randomization. The TS is used for safety analyses as well as demographics and baseline characteristics.
- Full Analysis Set (FAS): includes all patients in treated set who had non-missing baseline and at least one non-missing post-baseline and on-treatment measurement on any efficacy endpoint. Patients in FAS are analyzed according to the intent-to-treat

Boehringer Ingelheim		28 Mar 2019
BI Trial No.: 1346.9		
Doc. No.: c03559983-04	Trial Protocol	Page 66 of 116
		01 0001 1

principle, i.e., patients in FAS are analyzed under the randomized trial medication. The FAS is used for efficacy analyses.

Data from patients who were screened but not randomized will be listed but not included in any summary or inferential statistics. Specifications or important protocol violations will be provided in the TSAP.

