7.3.4 Safety analyses

Adverse events will be coded using the Medical Dictionary for Regulatory Activities (MedDRA) coding dictionary. Standard BI summary tables and listings will be produced. All adverse events with an onset between the start of treatment and the end of the residual effect period (REP), a period of 11 days after the last dose of trial medication, will be assigned to the treatment period for evaluation.

All treated patients will be included in the safety analysis and will be summarized under the actual trial medication received at randomization. In general, safety analyses will be descriptive in nature and will be based on BI standards. No hypothesis testing is planned.

Statistical analysis and reporting of adverse events will concentrate on treatment-emergent adverse events. To this end, all adverse events occurring between the start of treatment and the end of the residual effect period will be considered 'treatment-emergent'. The residual effect period is defined as 11 days after the last dose of trial medication. Adverse events that start before first drug intake and deteriorate under treatment will also be considered as 'treatment-emergent'.

Frequency, severity, and causal relationship of adverse events will be tabulated by system organ class and preferred term after coding according to the current version of the MedDRA. Frequency tables for all adverse events, protocol-specified adverse event of special interest (AESI), serious adverse event (SAE), adverse event leading to death, adverse event leading to discontinuation, investigator assessed drug-related adverse event and serious adverse event will be generated for treatment-emergent adverse events. In addition, summary statistics and descriptive analyses will be conducted for other safety parameters including worsening of disease state as assessed by PANSS and suicidality as assessed by C-SSRS.

Laboratory data will be analysed both quantitatively as well as qualitatively. The latter will be done via comparison of laboratory data to their reference ranges. Values outside the reference range as well as values defined as clinically relevant will be highlighted in the listings. Treatment groups will be compared descriptively with regard to distribution parameters as well as with regard to frequency and percentage of patients with abnormal values or clinically relevant abnormal values.

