#### 6.3 SUBJECT SETS ANALYSED

Screened Set (SS): •

> The screened set consists of all subjects who signed informed consent and were screened for the trial with at least one screening procedure done at Visit 1.

• Randomised Set (RS):

The randomised set consists of all subjects who were screened for the trial and who were randomised to trial treatment, regardless of whether any trial treatment was administered.

• Treated Set (TS):

The treated set consists of all subjects who were randomised and treated with at least one dose of trial treatment. The TS is used for the analysis of safety variables.

• Full analysis set (FAS):

The full analysis set consists of all randomised subjects who were treated with at least one dose of trial treatment and had a baseline and at least one evaluable post-baseline on-treatment measurement of the primary or secondary efficacy endpoints. The FAS is used for the primary and secondary analyses of the efficacy endpoints.

• Per protocol set (PPS):

The per protocol set is nested within the FAS and only includes subjects in the FAS who do not have any important protocol deviations which are specified to be excluded from the sensitivity analysis of the efficacy endpoints using the PPS (see Table 6.2: 1). If the number of subjects in the PPS is less than 90% of the number of subjects in the FAS, then the PPS is used for the sensitivity analysis of the primary and secondary efficacy endpoints.

• Ophthalmologic Sub-study Set (EYE):

The ophthalmologic sub-study set consists of all treated subjects who consented to participate in the ophthalmologic sub-study (including late/retrospective consent to the ophthalmologic sub-study) and had evaluable ophthalmologic measurements.

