#### 7.4 PRIMARY ENDPOINT

#### 7.4.1 Primary analysis of the primary endpoint

The MCPMod approach (6, 7) is implemented in two main stages: (1) trial design stage; (2) trial analysis stage. The procedures for the trial design stage, including the selection of candidate models covering a suitable range of dose-response shapes and sample size and power calculations are provided in the CTP Section 7.3.1 and 7.7. The procedures for the trial analysis stage are specified below. FAS is used for the primary analysis of the primary efficacy endpoint.

The change from baseline in MCCB overall composite t-score at Week 12 as well as the corresponding variance-covariance matrix are estimated using a mixed effects model repeated measure (MMRM) including the fixed categorical effects of treatment, visit and treatment-by-visit interaction, as well as the fixed continuous covariates of the baseline MCCB overall composite t-score and the baseline-by-visit interaction, and subject is considered as random effect. The unstructured covariance matrix is used to estimate the within subject errors. Then the pair-wise comparison procedure will be implemented using the optimal contrast tests which control the family-wise type I error rate at one-sided  $\alpha$ =0.05. The optimal contrasts corresponding to the candidate models are calculated as in the trial design stage and shown in

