#### 7.8.1 Adverse Events

Unless otherwise specified, the analyses of AEs will be descriptive in nature. All analyses of AEs will be based on the number of subjects with AEs and not on the number of AEs. The reporting and analyses of AEs will follow the BI guideline ( $\underline{8}$ ). AEs will be coded with the most current version of MedDRA®.

For analysis multiple AE occurrence data on the CRF will be collapsed into an AE provided that all of the following applies:

- All AE attributes are identical (lower level term (LLT), intensity, action taken, therapy required, seriousness, reason for seriousness, relationship, outcome)
- The occurrences were time-overlapping or time-adjacent (time-adjacency of 2 occurrences is given if the second occurrence started on the same day or on the day after the end of the first occurrence).

For further details on summarisation of AE data, please refer to (4, 8).

The analysis of AEs will be based on the concept of treatment emergent adverse events. That means that all adverse events occurring between the date of the first administration of trial treatment till the date of the last administration of trial treatment + residual effect period will be assigned to the on-treatment period label with the trial treatment assigned on Day 1 of the first treatment cycle. All AEs occurring before the first administration of trial treatment will be assigned to 'screening' and all AEs occurring after the residual effect period will be assigned to 'follow-up'. For details on the treatment definition, see Section 6.1.

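### SAP deviation code C1.1 analyses consistently mis-dispensed patients as treated without limiting this to safety, while the protocol analyses the FAS, and so the primary test, as randomised

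*SAP*

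**What the plan says.** **Protocol 7.3** gives each analysis set its own arm rule. For efficacy, "patients in FAS are analyzed under the randomized trial medication", under an intent-to-treat principle. For the treated set, which serves safety, demographics and baseline characteristics, "Patients in TS are analyzed under the actual trial medication received at randomization". Protocol 7.3.4 repeats the safety rule: treated patients are "summarized under the actual trial medication received at randomization".

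**SAP 6.3** defines who belongs to the FAS: "The full analysis set consists of all randomised subjects who were treated with at least one dose of trial treatment", with a baseline and an evaluable on-treatment efficacy measurement. It does not say under which arm they are analysed.

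**SAP 7.4.1** fixes the set for the main test: "FAS is used for the primary analysis of the primary efficacy endpoint".

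**SAP Table 6.2:1, code C1.1**, makes two checks. The first is whether each package had the correct content. The second is whether the dispensed packages match the randomised treatment. For a mismatch the instruction is "If not, and if treated consistently throughout the trial analyse as" treated (the last word falls after a break in the table). The exclusion column reads None.

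**SAP 7.8.1** labels on-treatment adverse events with "the trial treatment assigned on Day 1 of the first treatment cycle".

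**SAP Section 3** says the SAP rests on protocol Section 7. **SAP Section 4**, on changes to the planned analysis, lists only the SCoRS endpoint clarification.

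**The concern.** For a patient who consistently received another arm's kits, the two documents point to different arms in the primary analysis. Protocol 7.3 keeps the patient in the randomised arm. C1.1, read as written, places the patient in the arm received. Because the exclusion column reads None, the patient stays in the FAS, so the conflict reaches the MMRM treatment factor and the MCPMod contrasts built from it.

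Two things are at stake. An as-treated primary comparison is no longer fully randomised. And two competent analysts, one following C1.1 and the other protocol 7.3, would build different primary datasets. The rule should be fixed before unblinding, so that it cannot be chosen with the result in view.

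**Working it through.** **1. The texts side by side**

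| Source | Applies to | Arm used |
|---|---|---|
| Protocol 7.3 | FAS (efficacy) | Randomised |
| Protocol 7.3, 7.3.4 | Treated set (safety) | Actually received |
| SAP 6.3 | FAS | Not stated |
| SAP C1.1 | Kit and arm mismatch, no set named | Received, if consistent |
| SAP Section 4 | Declared changes | None on this point |

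In the SAP text available, C1.1 is the only explicit instruction on which arm to use for a mismatch.

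**2. The plan's own figure**

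Inputs: 75 evaluable per active arm, 150 on placebo, effect 0.35, one-sided alpha 0.05, average power 80% (protocol 7.7); contrasts from SAP Table 7.4.1:1. Dividing each contrast coefficient by its arm size recovers the six mean shapes, which are scaled to a maximum of 0.35. The critical value of the maximum contrast is 2.063 by normal approximation. Average power is then 82.0%, or 81.7% with the t distribution. Dropout: 75/0.9 = 83.3, rounded up to 84; placebo 2 × 84 = 168; total 4 × 84 + 168 = 504. The design reproduces within 2 points of power.

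**3. Leverage of one patient**

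Move one patient with value y from placebo (150 to 149) to 25 mg (75 to 76). The 25 mg versus placebo difference shifts by (y − mean at 25 mg)/76 + (y − placebo mean)/149. If y lies D SDs from both means:

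- Shift: D × (1/76 + 1/149) = D × (0.0132 + 0.0067) = 0.0199 D.
- Against the planned effect, at D = 1: 0.0199/0.35 = 5.7%.
- Against the standard error, √(1/75 + 1/150) = 0.1414: 0.0199/0.1414 = 14%.
- Linear-contrast z: numerator 0.762/76 + 0.593/149 = 0.0140. Standard error √[0.593²/150 + (0.212² + 0.085² + 0.127² + 0.762²)/75] = 0.1049. Shift 0.134 for each SD.

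This is leverage, not expected bias. If the patient simply responds as the 25 mg arm does, reassignment on average lowers the placebo mean by 0.35/150 = 0.0023 SD and leaves the 25 mg mean unchanged.

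**4. How often the two rules disagree**

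Assumptions: k patients, chosen at random, consistently receive another arm's drug (chance proportional to allocation) and respond to what they received; SD 1; the six shapes in rotation; critical value 2.064; 20,000 trials per setting. Arm means are compared without baseline adjustment or repeated measures.

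| Effect | k | Reject, as randomised | Reject, as treated | Rules disagree |
|---|---|---|---|---|
| 0.35 | 1 | 81.7% | 81.9% | 1.5% |
| 0.35 | 2 | 82.2% | 82.8% | 2.3% |
| 0 | 1 | 5.0% | 5.0% | 0.5% |
| 0 | 2 | 5.1% | 5.0% | 0.9% |

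A separate run of 12,000 trials per setting (critical value 2.067) gave disagreement of 1.5% and 2.3% at effect 0.35, and 0.6% and 0.8% with no effect. The simulation error of each power is √(0.82 × 0.18/20,000) = 0.27 points, so power above the 82.0% reference at k = 2 is noise.

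**The case against.** The strongest reply is that a default already exists. SAP Section 3 builds on protocol Section 7 and Section 4 declares no change, so silence in SAP 6.3 leaves the protocol's FAS rule in force. C1.1 is a comment in a deviation table whose output is an exclusion column, and it can be read as the treated-set rule. Some SAP sections are also absent from the public text. This shows that as-treated efficacy may not be intended, and it is why the point is a clarification. It does not remove the conflict: a general reliance on the protocol does not cancel an explicit instruction that names no set. Nor is the table a safety table. SAP 6.2 includes deviations that may influence the primary outcome, and some rows exclude from the per-protocol set.

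A second reply is rarity. Kits are assigned through the IRT at Visits 2 and 4, so a completer must receive the wrong arm's kit twice to count as consistently treated. That stands. It is why only one or two patients are illustrated; larger counts have no support in the documents.

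Three stronger readings are tempting and should not be drawn:

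- *That the SAP reverses the protocol, with efficacy as treated and adverse events as assigned.* This needs C1.1 to govern efficacy yet yield to SAP 7.8.1 for safety. If C1.1 has no limit, it covers safety too; if a more specific rule displaces it, the protocol's FAS rule does so for efficacy.
- *That version 4 of the SAP introduced the rule.* The history table says Table 6.2:1 was revised, but nothing shows that the C1.1 row changed.
- *That C1.1 sends mismatches to case-by-case exclusion.* The sentence "Otherwise, the cases will be described individually and possibly excluded" follows the package-content check; the mismatch check is introduced separately.

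**Conclusion.** The inconsistency is real and should be settled before unblinding. C1.1 gives an arm rule with no stated scope, the protocol gives a different one for the set that carries the primary test, and no change is declared.

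The practical effect is probably very small. With one or two consistently mis-dispensed patients, the choice of rule would change the proof-of-concept decision in about 1.5% to 2.3% of trials at effect 0.35, and in about 0.5% to 0.9% with no effect. A reader might infer an inflated error rate; the check does not support that, since type I error stays at about 5% under both rules when mix-ups are random. The harm is an undeclared choice between two primary datasets and the loss of a fully randomised comparison. The sizes rest on an assumed count, random mix-ups and patients responding to the drug received. The textual conflict rests on none of these.

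**What to change.** Add to C1.1 and to the FAS definition in SAP 6.3: *As treated applies to treated-set (safety) analyses only; all FAS efficacy analyses, including the primary MMRM/MCPMod, are as randomised.* If as-treated efficacy is really intended, declare it in SAP Section 4 with a reason.

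In the same edit, replace "the trial treatment assigned on Day 1 of the first treatment cycle" in SAP 7.8.1 with the protocol's rule, the actual medication received at randomisation. The trial has no treatment cycles, and the safety label should rest on what was received.

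The cost is wording only: no new analysis, and no patient leaves the FAS. As-randomised analysis keeps the usual slight dilution from mis-dispensing. In the simulation this was 0.2 points of power with one patient (81.9 − 81.7) and 0.6 with two (82.8 − 82.2), figures of the same order as the simulation error.
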